## 1.0 INTRODUCTION

Prior to surgery or other invasive procedures, skin must be treated with a topical antimicrobial product to minimize the risk of nosocomial infection by reducing the number of microorganisms on the skin. The Food and Drug Administration (FDA) Tentative Final Monograph (TFM) for *Topical Antimicrobial Drug Products for Over-the-Counter Human Use; Tentative Final Monograph for Healthcare Antiseptic Drug Products* (Vol. 59, No. 116, June 17, 1994 pp 31448 to 31450) describes *in-vivo* procedures for evaluating this type of product. Consistent with the 1994 TFM and The 2015 FDA TFM, 21 CFR Part 310, *Safety and Effectiveness of Health Care Antiseptics; Topical Antimicrobial Drug Products for Over-the-Counter Human Use; Proposed Amendment of the Tentative Final Monograph; Reopening of Administrative Record; Proposed Rule* (Vol. 80: No. 84, 1 May 2015. pp 25166 to 25205), recent letters published by the FDA on January 19, 2017 describe revised statistical analyses and expected performance criteria for antiseptic health care products tested in microbial log reduction studies: Revised criteria include use of a Negative Control and an FDA-approved NDA (new drug application) Active Control for comparison with the two Investigational Products. For assessment of immediate activity, a non-inferiority criterion with a 0.5 log10 margin is implemented for the mean treatment effect of the Investigational Products with the Active Control and a 1.2 log10 superiority criterion to the Negative Control. The mean treatment effect is determined from a linear regression of post-treatment log10 bacterial counts after correcting for baseline log10 bacterial loads. For a patient pre-operative skin preparation product, immediate efficacy is expected within 30 seconds and/or within 10 minutes post-application dry time on both the abdomen and the inguen. Persistence of efficacy is defined at 6 hours post-application as having  $\geq 0$  log10 reduction from baseline bacterial counts on abdomen and inguen at the 6-hour data points.

BD is evaluating the time dependent antimicrobial effectiveness of a single-use applicator containing octenidine dihydrochloride in isopropyl alcohol as a patient preoperative skin preparation product. Octenidine dihydrochloride in isopropyl alcohol is an antimicrobial solution for intact skin that produces antimicrobial effects against a wide range of microorganisms. Octenidine dihydrochloride has been shown to have broad antimicrobial activity against Gram-positive and Gram-negative bacteria and some fungi and maintains its activity in the presence of organic matter, such as blood or albumin.

## 2.0 OBJECTIVE

The primary objective of this study is to compare the immediate antimicrobial properties of octenidine dihydrochloride [OCT] in isopropyl alcohol - clear in a single-use applicator and octenidine dihydrochloride [OCT] in isopropyl alcohol - tinted in a single-use applicator to a Negative Control and an FDA NDA-approved Active Control. Single use applicators filled with 0.9% saline will serve as the Negative Control and Chloraprep® – Hi-Lite Orange® applicator will serve as the Active Control. In agreement with the Food and Drug Administration Tentative Final Monograph (TFM) for *Effectiveness Testing of a Patient Preoperative Skin Preparation*, a log10 reduction study will be used to determine antimicrobial efficacy based on the statistical analyses outlined in published letters from the FDA on January 19, 2017. The updated analysis applies a non-inferiority requirement of the investigative product to an FDA NDA-approved control with a 0.5 log10 margin and a 1.2 log10 superiority requirement over a Negative Control. The average treatment effect of the investigative products compared to the Active and the Negative Controls will be determined from a linear regression of post-treatment log10 bacterial counts after correcting for pre-treatment log10 bacterial loads. The secondary objective is to determine the persistent antimicrobial activity of the two Investigative Products, Active Control, and the Negative Control. Log10 bacterial counts at 6 hours for each treatment site will be converted to a binary (yes or no) success measure with success defined as having skin flora counts that are less than or equal to the baseline skin flora counts. The objective is to demonstrate a success proportion  $\geq 95\%$  on both the abdomen and the inguen with 95% confidence.

Testing will be performed according to the procedures outlined in the Food and Drug Administration Tentative Final Monograph (TFM) for *Effectiveness Testing of a Patient Preoperative Skin Preparation* (FR 59:116, 17 June 94, pp. 31450-31452). The test methods for this evaluation will be based on ASTM Standard Test Method E1173-15,

*Evaluation of Preoperative, Precatheterization, or Preinjection Skin Preparations and the test criteria from the deferral letters published by the FDA on January 19, 2017.*

## **6.0 CLINICAL RESEARCH STANDARDS**

The clinical investigation, including the informed consent, will be approved by the Gallatin Institutional Review Board (GIRB) in accordance with Title 21 of the Code of Federal Regulations, Parts 50, 56, 58, 312, and 314, and in accordance with the International Conference on Harmonisation (ICH) guidelines. The written approval of the Board will be obtained prior to the initiation of the study.

The study will be conducted in accordance with Good Clinical Practice regulations, Good Laboratory Practice regulations, the Standard Operating Procedures of BioScience Laboratories, Inc., the study protocol, any protocol amendments, and the regulatory requirements of the United States Food and Drug Administration (FDA) and ICH.

## 7.0 SCOPE

The objective of this study is to compare the immediate and persistent antimicrobial properties of octenidine dihydrochloride [OCT] in isopropyl alcohol - clear in a single-use applicator and octenidine dihydrochloride [OCT] in isopropyl alcohol - tinted in a single-use applicator to a Negative Control, 0.9% saline applied with a single use applicator, and an FDA-approved Active Control, ChloraPrep® – Hi-Lite Orange® applicator. Testing will be performed according to the procedures outlined in the Food and Drug Administration Tentative Final Monograph (TFM) for *Effectiveness Testing of a Patient Preoperative Skin Preparation* (FR 59:116, 17 June 94, pp. 31450-31452). The test methods for this evaluation will be based on ASTM E1173-15, *Standard Test Method for Evaluation of Preoperative, Precatheterization, or Preinjection Skin Preparations* and the test criteria from the deferral letters from the FDA published on January 19, 2017.

A sufficient number of male and female, overtly healthy, volunteer subjects at least 18 years of age, will be enrolled in the screening phase to ensure that the total numbers of evaluable samples collected from inguinal and abdominal regions meet or exceed 36 evaluable test sites per test material (total minimum of 144 each for inguinal and abdominal regions). Subjects must satisfy all Screening Day and Treatment Day Inclusion/Exclusion Criteria prior to screening sample collection and Treatment Day procedures. If the required numbers of subjects do not qualify from the initial screening group, additional volunteers will be recruited.

Following a 14-day restriction period, subjects with resident bacterial flora that meet the specified criteria will be eligible to proceed to the treatment phase of testing. Specific baseline criteria for subjects will be  $\geq 3.00 \log_{10}$  CFU/cm^2 from the skin of the abdomen and  $\geq 5.00 \log_{10}$  CFU/cm^2 from the skin of the inguen. Evaluations will consist of samples collected at baseline, 30 seconds  $\pm$  5 seconds, 10 minutes  $\pm$  30 seconds, and at 6 hours  $\pm$  30 minutes post-treatment. All plating for this study will be conducted in duplicate using the pour-plating technique and incubated at  $30 \pm 2$  °C for 72 hours  $\pm$  4 hours. The left and right abdominal test sites will be 5"  $\times$  5" areas of skin.

The abdominal sampling sites will not include skin that shows evidence of the subjects clothing waistband. The test sites on the left and right inguina will be 2"  $\times$  5" areas of skin that appear to be similar in condition. Subjects passing into the treatment phase of testing will be treated on bilateral abdomen and/or inguen sites and sampled for baseline microbial populations prior to treatment and at the indicated post-treatment time points on randomly assigned sites of each test area. Each subject who chooses to participate in

this study will be required to remain at the test facility for scheduled Treatment to include 30 seconds, 10 minutes, and 6 hours post-prep sampling.

## 7.1 Primary Analysis

The primary purpose of the study is to compare the immediate antimicrobial activity of the Investigational Products to the Negative Control and Active Control according to the methods described in the FDA TFM with the statistical analyses outlined in a deferral letter published January 19, 2017. A linear regression model will be used for primary analysis. In the model, the response is the post-treatment  $\log_{10}$  bacterial counts and predictors are the treatment effect and the pre-treatment  $\log_{10}$  bacterial counts as a covariate. The interaction between the treatment and pre-treatment  $\log_{10}$  bacterial counts will also be explored. If there is no significant interaction detected between treatment and pre-treatment  $\log_{10}$  bacterial counts, the interaction term will be removed from the model and the average difference between treatments will be estimated from the linear regression model after correcting for pre-treatment bacterial loads. If there is a significant interaction detected between treatment and pre-treatment  $\log_{10}$  bacterial counts, the average difference between treatments will be estimated from the linear regression model after averaging over the interaction term. The objective is to ensure that the Investigational Products mean treatment effects are non-inferior to the FDA-approved NDA Active Control, within a 0.5  $\log_{10}$  margin for both the abdomen and inguen at 30 seconds and 10 minutes after application; the Investigational Products must have a mean treatment effect of at least 1.2  $\log_{10}$  greater than that for the Negative Control for both the abdomen and inguen at 30 seconds and/or 10 minutes after application. The 95% confidence intervals will be summarized for each product tested, grouped by anatomical site and the post-application time points: 30 second and 10 minute.

Primary analyses will be based on the modified Intent to Treat (mITT) data set with supportive analysis conducted using the Per Protocol data set, as described in Section 15.0. It is expected that the mean treatment effect will meet the standards above, however this is a Phase II study to inform design of future efficacy studies and is not designed to provide statistically powered evidence of efficacy, and the confidence intervals may not lie entirely above the described targets.

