#### 15.0 STATISTICAL METHODS

Data processing and statistical analysis for this study will be conducted by the BD statistical group based on the final monitored data provided by BSLI to the BD statistical group.

Details of the statistical analysis will be provided in a separate statistical analysis plan.

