## 15.1 Primary Analysis

An Analysis of Variance (ANOVA) of the baseline  $\log_{10}$  CFU/cm^2 values will be performed separately for abdomen and inguen to determine whether the randomization resulted in treatment arms with similar treatment day baseline CFU/cm^2 values.

The primary purpose of the study is to compare the immediate antimicrobial activity of the Investigational Products to the Negative Control and Active Control according to the methods described in the FDA TFM using the statistical analyses outlined in the deferral letters published by the FDA on January 19, 2017. A linear regression model will be used for primary analysis. In the model, the response is the post-treatment  $\log_{10}$  bacterial counts and predictors are the treatment effect and the pre-treatment  $\log_{10}$  bacterial counts as a covariate. The interaction between the treatment and pre-treatment  $\log_{10}$  bacterial counts will also be explored. If there is no significant interaction detected between treatment and pre-treatment  $\log_{10}$  bacterial counts, the interaction term will be removed from the model and the average difference between treatments will be estimated from the linear regression model after correcting for pre-treatment  $\log_{10}$  bacterial counts. If there is a significant interaction detected between treatment and pre-treatment  $\log_{10}$  bacterial counts, the average difference between treatments will be estimated from the linear regression model after averaging over the interaction term. The objective is to achieve a mean treatment effect ( $\log_{10}$  reduction) for Investigational Products no less than that for the Active Control by more than 0.5  $\log_{10}$  and at least 1.2  $\log_{10}$  greater than that for the Negative Control on both the abdomen and inguen. The 95% confidence intervals will be summarized for each product tested, grouped by anatomical site and each post-application time point (30 seconds and 10 minutes) and compared to the non-inferiority margin of 0.5  $\log_{10}$  for Investigational Products vs. Active Control and compared to the superiority margin of 1.2  $\log_{10}$  for Investigational Products vs. Negative Control.

It is expected that the treatment effects will meet the standards outlined above, however this is a Phase II study to inform design of future efficacy studies and is not designed to provide statistically powered evidence of efficacy.

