### **16.2 Alteration of the Study**

Neither the Investigator, nor the Sponsor, will modify or alter this protocol without first obtaining the concurrence of the other parties. All protocol modifications including, but not limited to changes in the Principal Investigator, inclusion/exclusion criteria, number of subjects to be enrolled, study sites, or procedures must be submitted to the GIRB as a written amendment for review and approval prior to implementation, with one exception: when necessary to eliminate an apparent immediate hazard to the subject.

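### Protocol 7.1 lets superiority over the Negative Control be met at either time point, SAP 7.3.1 tests it at both, and neither states how the times combine, although the SAP's no-multiplicity statement depends on it

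*Protocol*

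**What the plan says.** Protocol 7.1 uses two time rules in one sentence. Non-inferiority to the Active Control must hold within a 0.5 log10 "margin for both the abdomen and inguen at 30 seconds and 10 minutes after application". The superiority requirement is put as a size: "the Investigational Products must have a mean treatment effect of at least 1.2" (in log10 units, relative to saline). Where and when it must be met is worded differently from the non-inferiority clause: "Negative Control for both the abdomen and inguen at 30 seconds and/or 10 minutes after application". Protocol 1.0 uses the looser form as well: "immediate efficacy is expected within 30 seconds and/or within 10 minutes post-application dry time on both the abdomen and the inguen".

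Protocol 15.1 asks for 95% confidence intervals "grouped by anatomical site and each post-application time point (30 seconds and 10 minutes) and compared to the non-inferiority margin of 0.5" log10, and "compared to the superiority margin of 1.2" log10 for the Negative Control comparison. It gives no rule for combining the two times. Protocol 15.0 defers to the SAP: "Details of the statistical analysis will be provided in a separate statistical analysis plan".

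SAP 7.3.1 sets both comparisons at 30 seconds and 10 minutes. Its hypotheses are written on the 95% confidence bounds: upper bound of IP - AC below 0.5, lower bound of NC - IP above 1.2. It then says that success requires both criteria on both body sites, and concludes from this that no multiplicity adjustment is required. That sentence names neither the time points nor the two products. SAP 7.3 sets alpha at 5% two-sided for all analyses. Mock Tables 5 and 6 give a Yes or No per product and time, and no overall verdict.

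**The concern.** The two documents can give different answers on the same data. Mock groin Table 6 happens to show the pattern: NC - IP2 is No at 30 seconds (0.90 to 1.50) and Yes at 10 minutes (1.28 to 1.91). Protocol 7.1 would count superiority as met at that site; a both-times reading of the SAP would not. The table is a one-site placeholder and only illustrates the difference. IP2 would fail overall either way, because its upper bound against the Active Control at 10 minutes in Table 5 is 1.39.

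The SAP's reason for not adjusting is that every component must pass. For one product that argument covers the time points only if both must pass. If either suffices, superiority at a site gets two chances at 2.5% one-sided. A product could then be declared successful on a rule that the stated error control does not cover. If the rule is chosen after the counts are linked to product, it can also look chosen to fit the result.

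**Working it through.** **Inputs from the documents.** Alpha 5% two-sided (SAP 7.3), so 0.05/2 = 2.5% for each directional test. Margins 1.2 and 0.5 log10. 36 evaluable sites per product per region.

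**Assumptions (the documents give none of these).** Residual SD, true differences, and the correlation r between the 30-second and 10-minute statistics. Triples below are for r = 0 / 0.5 / 0.9. Standard errors treat the arms as unpaired.

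**1. Both times required.** All components must pass, so the worst case has one component at its boundary and the rest certain to pass. The error is 2.5% per product, and the SAP statement is sound for that product.

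**2. Either time sufficient, superiority alone.** Worst case: one site truly at 1.2 at both times, the other site clearly superior.

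Error = 1 - P(Z1 < 1.96, Z2 < 1.96), bivariate normal with correlation r = **4.94% / 4.54% / 3.52%**.

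At r = 0 this is 1 - 0.975² = 4.94%. With 97.5% two-sided intervals the critical value is 2.24, and the error is 2.48% / 2.32% / 1.81%.

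**3. Either time sufficient, non-inferiority also required at both times and sites.** 500,000 simulated trials per setting, with the IP arm shared by both contrasts:

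| Assumed setting | Error of declaring success |
|---|---|
| SD 1.0, IP = AC | 0.8 / 1.3 / 1.5% |
| SD 0.7, IP = AC | 3.1 / 3.3 / 2.9% |
| SD 1.0, IP 0.3 log10 better than AC | 3.9 / 3.8 / 3.1% |
| SD 0.7, IP 0.1 worse | 1.5 / 2.0 / 2.0% |
| SD 1.3, IP = AC | 0.2 / 0.5 / 0.8% |
| SD 0.5, IP 0.1 worse | 3.9 / 3.9 / 3.1% |

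The error falls on both sides of 2.5%.

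**4. How often the rules disagree at one site.** SE = SD × √(2/36) = 0.165, 0.236, 0.306 at SD 0.7, 1.0, 1.3. To pass, the observed NC - IP difference must exceed 1.2 + 1.96 × SE = 1.52, 1.66, 1.80. The chance that exactly one time passes, with the same true difference at both times, is:

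| True NC - IP | SD 0.7 | SD 1.0 | SD 1.3 |
|---|---|---|---|
| 1.7 | 24 / 18 / 8% | 49 / 33 / 14% | 47 / 31 / 14% |
| 2.0 | 0.4 / 0.4 / 0.2% | 14 / 11 / 5% | 38 / 26 / 12% |
| 2.2 | under 0.1% | 2.2 / 1.9 / 1.0% | 17 / 13 / 6% |
| 2.5 | under 0.1% | under 0.1% | 2.2 / 1.9 / 1.0% |

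Disagreement is common only when the true difference is near the pass threshold.

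**5. Two products.** Even with both times required, the chance that at least one of the two products passes falsely can reach 4.5%, taking a correlation of 0.5 from the shared Negative Control (the step 2 formula at r = 0.5).

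**The case against.** The best reply is that the SAP already settles the matter. The Protocol delegates analysis details to it, it tests each criterion at both times, and the natural reading is that both must pass. On that reading the no-adjustment statement is right for each product, and what remains is a wording mismatch. That is a fair account of the SAP, but the SAP never states the rule. Nor does anything in either document say that it overrides an explicit criterion in the Protocol.

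A second reply is that success is never declared on superiority alone, so step 2 overstates the error. This partly stands: with non-inferiority required, several settings fall well below 2.5%. In the two settings above 2.5% at SD 0.7 and 1.0, the Active Control itself lies only 1.2 or 0.9 log10 from saline at the boundary site. But that is not a general limit. At SD 0.5 with the product 0.1 worse, the Active Control is 1.3 from saline and the error is still 3.1% to 3.9%.

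It is also true that adjustment would be unnecessary with a single pre-specified time, but neither document names one. Protocol 7.1 may mean its 1.2 as a target for the mean, since it warns that intervals may not clear the targets. Yet Protocol 15.1 and SAP 7.3.1 compare intervals with the margins, so the sections still need to agree.

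Finally, the study is unpowered, is meant to inform later trials, and reports every interval, so a reader could apply either rule. This limits the consequence. It does not remove the conflict, because the SAP states formal hypotheses and says when the study will declare success.

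**Conclusion.** The concern holds and should be fixed. The conflict between Protocol 7.1 and SAP 7.3.1 is in the current text and depends on no assumption. The SAP's no-adjustment statement is assured per product under a both-times rule and is not assured under an either-time rule.

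The size of the error does rest on assumption. Under an either-time rule, the superiority criterion alone can reach about twice the nominal 2.5%. With non-inferiority added, the settings examined gave about 0.2% to 3.9%. The practical effect is confined to the declaration of success and the truth of the multiplicity statement; no data or estimates change.

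**What to change.** State one combining rule in Protocol 7.1, Protocol 15.1 and SAP 7.3.1, before plate counts are linked to product, and say that the 95% confidence bound decides.

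- **Simplest option: both times.** Replace *and/or* with *and* in the superiority clause of Protocol 7.1. Add to the SAP: *For each Investigational Product separately, success requires non-inferiority and superiority at both 30 seconds and 10 minutes on both abdomen and groin; error is controlled per product.* The no-adjustment sentence can then stay, limited to each product.
- **If either time is to suffice.** Use 97.5% two-sided intervals per time point for superiority and remove the no-adjustment statement. Say also whether the passing time must be the same on both body sites, which Protocol 7.1 leaves open.

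In either case, align the *and/or* in Protocol 1.0 or mark it as background and not the study's decision rule.

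The cost is one phrase, two sentences and a note, plus the approval process. Protocol changes "must be submitted to the GIRB as a written amendment for review and approval prior to implementation" (Section 16.2), and Section 18.0 also requires the sponsor's written approval. No subjects or samples are added. The both-times rule is stricter than the present Protocol 7.1, and the choice is the sponsor's provided the sections agree.

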## 7.2 Secondary Analysis

The secondary objective is to determine the persistent antimicrobial activity of the two Investigative Products, Active Control, and Negative Control.  $\log_{10}$  bacterial counts at 6 hours for each treatment site will be converted to a binary (yes or no) success measure with success defined as having skin flora counts that are less than or equal to the baseline skin flora counts. The objective is to demonstrate a success proportion  $\geq 95\%$  on both the abdomen and the inguen with 95% confidence.

